Evaluation of an Artificial Intelligence-Assisted, Image-Based Dietary Assessment Tool in the Framingham Heart Study

NCT06455111

[name]

[contact]

Statistical Analysis Plan pages 3-4

Evaluation of an Artificial Intelligence-Assisted, Image-Based Dietary Assessment Tool in the Framingham Heart Study

Background: Assessment of dietary intake in large, free-living populations is inherently challenging due to the complex nature of human diet. Advancements in traditional methods of dietary assessment (i.e., web-based dietary recalls or records) have aimed at improving data accuracy while reducing participant burden. Further utilizing food recognition technologies to capture real-time food intake may aid in overcoming limitations of existing methods. Keenoa[□], an artificial intelligence-enhanced, image-assisted tool, is a newly designed mobile application that may facilitate collection of dietary data.

Aims: Primarily, we will assess acceptability and usability of Keenoa compared with the traditional, web-based Automatic Self-Administered 24-Hour (ASA24) Dietary Assessment Tool in the Framingham Heart Study Third Generation-based cohorts at examination 4. We will also determine the proportion of participants who complete all three days of dietary assessment with energy intake >600 kcal, either through Keenoa or ASA24.

Methods: With a randomized block design, this study will take place as part of the Framingham Heart Study (FHS) glucose study (R01 DK129305). We currently ask participants from the Third Generation-based cohorts, at their fourth examination, to wear Dexcom G6 Pro continuous glucose monitor on either their arm or abdomen for a duration of at least 4 days. During this time, we request participants to complete 3 consecutive days of dietary record through ASA24. For the purpose of this trial, we will randomize the dietary assessment tool weekly between ASA24 and Keenoa, therefore, depending on the week of administration, participants are randomized to either a 3-day dietary record via ASA24 or a 3-day dietary record through Keenoa. This trial will last a total of 6 weeks.

Background and Rationale

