Aim 2: Determine the response rates; defined as the proportion of participants who complete all three days of diet assessments with energy intake >600 kcal, either through KeenoaTM or ASA24. We hypothesize that Keenoa will have higher response rate for those completing 3-day diet records.

Methods

We will conduct a randomized block trial, recruiting participants from the Third Generation-based cohorts, at their fourth examination. For the purpose of this trial, we will randomize the dietary assessment tool weekly between ASA24 and KeenoaTM, therefore, depending on the week of administration, participants are randomized to either a 3-day dietary record via ASA24 or KeenoaTM. Refer to **Figure 1** for complete description of enrollment process.

During the weeks when KeenoaTM is administered: we will ask the participants if they have a smartphone. If not, individuals will not be eligible to participate in the trial, but they can still complete ASA24 dietary records, allowing their dietary information be collected for the FHS Glucose Monitoring Study. Then we will ask participants if they have a Google Play ID (for Android users) or Apple ID (for IOS users). If yes, our research technician at FHS center will help participants in setting up KeenoaTM. If not, we will provide participants with at home instruction protocol.

Statistical Analysis Plan

Power calculation: We estimate that we will require ~50 participants per group to complete aims 1 and 2.

Over the first 8 months of the current exam, we have had a response rate of 62.1% of participants completing 3 days of diet record using ASA24. We estimate that KeenoaTM would have an 80% response rate among our participants, therefore, considering alpha=.05, and 80% power, the sample size required is 50 participants per group.

Aim 1 analysis:

We will use chi-square to evaluate whether the average satisfaction rate (out of 5) of the two instruments (Keenoa vs. ASA24) is statistically significantly different.

Aim 2 analysis:

We will use chi-square to evaluate whether the response rates, defined as the percentage who completed 3 days of dietary assessment with energy intake >600 kcal, from the two instruments (Keenoa vs. ASA24) are statistically significantly different.

We will generate a summary of participant characteristics using descriptive statistics.

References:

1. Willett W. *Nutritional epidemiology*. Oxford university press; 2012.

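### The figure of about 50 per group is claimed for Aims 1 and 2, but no Aim 1 assumption enters it, so the size claim for the primary aim has no stated basis

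*Combined protocol and SAP*

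**What the plan says.** The Power calculation paragraph of the Statistical Analysis Plan opens with a claim that covers both aims: "We estimate that we will require ~50 participants per group to complete aims 1 and 2". Its justification concerns response rates only. For ASA24, "we have had a response rate of 62.1% of participants completing 3 days of diet record using ASA24"; Keenoa, it is estimated, "would have an 80% response rate among our participants"; and from these, "considering alpha=.05, and 80% power, the sample size required is 50 participants per group".

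The Aims paragraph of the summary puts acceptability first: "Primarily, we will assess acceptability and usability of Keenoa". Specific Aims states the Aim 1 hypothesis, that Keenoa is more acceptable than ASA24 on a 0-5 satisfaction scale. The Aim 1 analysis is a chi-square test of the average satisfaction score, with no categories or cut-point given. The summary and Methods say that the tool is randomised by week, and the summary gives a duration of 6 weeks.

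**The concern.** A sample-size statement tells readers what the trial can detect. Here it covers the primary aim, but nothing in the calculation concerns that aim: no satisfaction difference, SD or proportion of satisfied participants appears anywhere in the documents. A reader would take the stated 80% power to apply to Aim 1 and might give a non-significant satisfaction comparison more weight than the design supports.

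The figure cannot be borrowed from Aim 2 as a checked size either, because the Aim 2 inputs do not produce it.

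**Working it through.** **1. The plan's own figure.** Inputs from Power calculation: p1 = 0.621, p2 = 0.80, alpha 0.05, power 80%, equal groups. Sidedness is not stated. The Aim 2 test asks whether the rates "from the two instruments (Keenoa vs. ASA24) are statistically significantly different", so two-sided is taken first. The pooled-variance formula is

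n = [1.960 × √(2·p̄·(1 − p̄)) + 0.842 × √(p1(1 − p1) + p2(1 − p2))]² / (p2 − p1)²

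With p̄ = 0.7105, this is (1.960 × √0.4114 + 0.842 × √0.3954)² / 0.179² = 3.191 / 0.03204 = 99.6, so 100 per group.

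| Variant | Two-sided | One-sided |
|---|---|---|
| Pooled | 100 | 79 |
| Pooled, continuity-corrected | 111 | 90 |
| Unpooled | 97 | 77 |
| Arcsine | 99 | 78 |

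None of these gives 50. Power at 50 per group is 50.5% two-sided and 63% one-sided.

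**2. Inputs for Aim 1.** From the documents: 50 per group, alpha 0.05, 80% power, a 0-5 scale. Not in the documents: the expected difference, the SD, and the categories for the chi-square. The steps below therefore use a comparison of means and give results in SD units.

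**3. Individual-level two-sample t-test, 50 v 50.** Detectable difference d = λ × √(1/n1 + 1/n2), where λ is the noncentrality giving 80% power. With 98 df, λ = 2.829 and d = 2.829 × √(2/50) = 0.566 SD. In scale points this is 0.45, 0.57, 0.68 or 0.85 for an assumed SD of 0.8, 1.0, 1.2 or 1.5. By the normal approximation, power is 32% at 0.3 SD, 71% at 0.5 SD and 98% at 0.8 SD.

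**4. Fewer ratings (assumption).** If only expected completers rate the tool, the numbers are 0.621 × 50 = 31 and 0.80 × 50 = 40. With 69 df, λ = 2.841 and d = 2.841 × √(1/31 + 1/40) = 0.68 SD. The documents do not say who will be asked to rate.

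**5. Comparison between randomised weeks (assumption).** Assume three weeks per tool and equal weeks of 100/6 = 16.7 participants. The t-test then has 4 df and λ = 3.761. The design effect is DE = 1 + 15.7 × ICC (intraclass correlation), and d = 3.761 × √(2 × DE/50).

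| ICC (assumed) | DE | d, week-level, 4 df | d, individual-level df with DE |
|---|---|---|---|
| 0 | 1.00 | 0.75 | 0.57 |
| 0.01 | 1.16 | 0.81 | 0.61 |
| 0.02 | 1.31 | 0.86 | 0.65 |
| 0.05 | 1.78 | 1.00 | 0.76 |

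**6. The planned chi-square.** With 100 participants in all and 80% power, the detectable effect size w is 0.28 on 1 df, 0.35 on 4 df and 0.36 on 5 df. Which applies cannot be settled without the categories.

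**The case against.** A reader might infer that the trial can detect only a large satisfaction difference. The documents do not support that. At 50 ratings per group, the individual-level figure of 0.57 SD lies just above the conventional medium value (0.5) and well below large (0.8), where power is 98%. The documents give neither an SD nor a smallest important difference on the 0-5 scale by which to call it large. The range of 0.75 to 1.0 SD needs a week-level analysis, a 3 v 3 split, equal weeks and ICC values, none of which the plan states. At an ICC of 0, the rise from 0.57 to 0.75 SD comes entirely from having 4 df. These points stand, so the larger figures are conditional, as is the completer-only figure.

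It can also be said that a t-test is not the planned test. That is true, but the planned chi-square has no categories, so its power cannot be fixed. The Aim 2 arithmetic says nothing about Aim 1 power; it shows only that 50 is not a checked figure to carry across, and its correction is a separate point. Finally, the plan hypothesises superiority and nowhere proposes to claim equal acceptability from a null result. The risk is therefore one of misreading, not of a planned false claim.

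None of this supplies an Aim 1 basis for the figure.

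**Conclusion.** The concern holds as a point about an unsupported claim. The documents present about 50 per group as the requirement for both aims, give no Aim 1 input, and quote Aim 2 inputs that need about 100 per group. For a comparison of satisfaction means at 50 per group, the difference detectable with 80% power is about 0.57 SD by an individual-level t-test. It is about 0.75 to 1.0 SD between randomised weeks, and about 0.68 SD at the individual level if only expected completers rate, each under the assumptions shown in the working. Any translation into scale points rests on an assumed SD. The trial may still be worth running at this size; what is unsupported is the statement that the size meets the need of Aim 1.

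**What to change.** Amend the Power calculation and Aim 1 analysis text as follows.

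- Remove Aim 1 from the sample-size claim and state that no satisfaction assumption entered the figure.
- Do not replace the claim with a statement that 50 was derived from Aim 2, as if that derivation were sound. State that the quoted Aim 2 inputs do not reproduce 50. If the separate Aim 2 correction changes the size, recompute the Aim 1 figures.
- Give the Aim 1 difference detectable with 80% power at 50 per group: about 0.57 SD by an individual-level t-test, and about 0.75 to 1.0 SD between randomised weeks, with the assumptions on week split, week size and ICC stated. Note that fewer ratings raise it, for example to 0.68 SD at 31 v 40. Say that these figures are for a comparison of means.
- Report Aim 1 as a mean difference with a 95% confidence interval, and state that a non-significant result will not be read as evidence of equal acceptability.

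The cost is SAP wording only; this point by itself asks for no change in enrolment. The downside is that the stated capability of the trial becomes less favourable.

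### Does the 62.1% ASA24 rate behind the power calculation fail to match the trial's own endpoint and eligible population?

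*Combined protocol and SAP*

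**What the plan says.** The power calculation in the Statistical Analysis Plan rests on two rates. The control rate is historical: "Over the first 8 months of the current exam", it says, "we have had a response rate of 62.1% of participants completing 3 days of diet record using ASA24". The Keenoa rate is a judgement: "We estimate that KeenoaTM would have an 80% response rate among our participants". From these the plan concludes, "considering alpha=.05, and 80% power, the sample size required is 50 participants per group".

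Under Specific Aims, Aim 2 introduces response rates as a defined term, "defined as the proportion of participants who complete all three days of diet assessments with energy intake >600 kcal", and the Aim 2 analysis repeats the kcal condition.

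Under Methods, the paragraph on the weeks when Keenoa is administered has staff ask about smartphone ownership. For those without one: "If not, individuals will not be eligible to participate in the trial, but they can still complete ASA24 dietary records". The text describes no such question for ASA24 weeks. Figure 1, cited for the full enrolment process, is not reproduced in the text available.

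**The concern.** A control rate used for planning should be measured on the trial's outcome, in the people the trial will enrol. Read literally, the 62.1% counts people who recorded three days, whatever energy intake they reported, in a period when ASA24 was the tool in use and no smartphone screen is mentioned. The endpoint is narrower because each day must exceed 600 kcal. The population is narrower too, if ownership is required in both arms.

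If the kcal rule was not applied, applying it could only lower the rate or leave it unchanged. Restricting to smartphone owners might move it in either direction. The planned difference of 80 − 62.1 = 17.9 percentage points would then not be a difference on the trial's own outcome. Required size is sensitive to the control rate in this region, so the power statement could remain wrong even after its arithmetic is put right.

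**Working it through.** **Inputs.** From the power paragraph: control 62.1%, Keenoa 80%, alpha 0.05, power 80%, 50 per group. Sidedness is not stated. The Aim 2 analysis asks whether the rates "from the two instruments (Keenoa vs. ASA24) are statistically significantly different", which has no direction, so two-sided is assumed. Participants are treated as independent and the groups as equal.

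**The plan's own figure.** The pooled two-proportion formula is

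n per group = [z₀.₉₇₅ √(2p̄(1−p̄)) + z₀.₈₀ √(p₁(1−p₁) + p₂(1−p₂))]² / (p₂−p₁)²

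With p₁ = 0.621, p₂ = 0.80 and p̄ = 0.7105:

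- first term: 1.960 × √0.4114 = 1.257
- second term: 0.842 × √0.3954 = 0.529
- n = (1.257 + 0.529)² / 0.179² = 3.191 / 0.03204 = 99.6, so 100 per group

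The stated 50 does not reproduce. Power at 50 per group is 50.5% by the normal approximation and 51.1% by exact enumeration of the chi-square test. At 100 per group it is 80.2% and 80.6%. This shortfall arises with 62.1% taken at face value, so it does not depend on where that figure came from.

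**Sensitivity to the control rate.** The documents give no alternative rate, so the range below is assumed. Two ways of varying it are shown (two-sided, 80% power; power is exact).

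| ASA24 rate | n per group, Keenoa fixed at 80% | Power at 50 per group | Power at 100 per group | n per group, gap fixed at 17.9 points |
|---|---|---|---|---|
| 58% | 69 | 67% | 93% | 108 |
| 60% | 82 | 60% | 88% | 104 |
| 62.1% | 100 | 51% | 81% | 100 |
| 66% | 157 | 35% | 61% | 91 |
| 70% | 294 | 21% | 37% | 81 |

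Both power columns hold Keenoa at 80%. With Keenoa fixed, a few points either way moves n by dozens. With the gap fixed, the whole range moves n by 108 − 81 = 27, and in the opposite direction: a higher control rate needs fewer people. Neither column is privileged. The kcal rule applies to both tools, and the 80% is itself an estimate made with the 62.1% in view, so revising one rate might well mean revising the other.

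**Endpoint wording, side by side.** Aim 2 defines response rates with the kcal condition. Its next sentence states the hypothesis in shorthand, referring to the response rate among those completing three-day records without repeating the condition. The power sentence uses the same term in the same short form, and the Aim 2 analysis then gives the definition in full. The 62.1% may therefore already include the condition. The documents do not settle it.

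**Population, side by side.** The exclusion for lacking a smartphone stands in the Keenoa-week paragraph. As written, people attending in an ASA24 week are asked nothing about phones, which is also how the 62.1% appears to have been obtained. The denominator is not stated. The Methods summary on the opening page suggests exam 4 participants wearing a glucose monitor, not everyone attending the exam.

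**The case for a change.** The strongest case for acting is that the plan states the kcal condition whenever it formally defines the endpoint, yet leaves it out beside the one empirical number in the power calculation. A reader cannot tell whether it was applied. The 80% for Keenoa can only describe smartphone owners, so the 17.9-point gap may set an unrestricted rate against a restricted one. Correcting the sample size to 100 per group would not cure this: power there would be 61% if the true ASA24 rate were 66% and Keenoa stayed at 80%. The sponsor holds the records, and checking them would be cheap.

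Part of this stands. The numerator, denominator and smartphone status behind the 62.1% are not given, and stating them would be good reporting. But not shown to match is weaker than does not match, and only the weaker statement is supported. The 61% depends on an assumed control rate with Keenoa unchanged. If ownership is asked in one arm only, the issue is comparability of the arms, which a better-sourced control rate would not repair.

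**Conclusion.** No change to the plan follows. This is missing detail about one planning input, and the documents do not show the input to be wrong. The defined term reasonably carries the kcal condition, the smartphone screen is described only for Keenoa weeks, and any claim that the 62.1% covers all exam participants is an inference.

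The figure enters no analysis. The Aim 2 chi-square test will use the rates observed in the two arms, so neither the test nor its conclusion depends on the 62.1%.

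The possible effect on planning cannot be fixed from the documents. Over an assumed ASA24 rate of 58% to 70%, the size needed runs from 69 to 294 per group with Keenoa held at 80%, or from 108 down to 81 with the gap held at 17.9 points. These figures assume a two-sided test, equal groups and independent participants. The demonstrable fault in the paragraph, 50 per group where about 100 are needed, is a separate point and stands without this one.

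### Fifty per group does not give 80% power for 62.1% vs 80%: the planned chi-square test needs about 100 per group (two-sided), and 50 per group gives about 51% power.

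*Combined protocol and SAP*

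**What the plan says.** The Power calculation paragraph of the Statistical Analysis Plan opens with a single size for both aims: "We estimate that we will require ~50 participants per group to complete aims 1 and 2". It then gives the basis. The ASA24 figure is drawn from the exam's initial 8 months, for which the plan reports: "we have had a response rate of 62.1% of participants completing 3 days of diet record using ASA24". Keenoa, it assumes, "would have an 80% response rate among our participants". The conclusion is: "considering alpha=.05, and 80% power, the sample size required is 50 participants per group".

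The Aim 2 analysis is a chi-square test of whether the response rates "from the two instruments (Keenoa vs. ASA24) are statistically significantly different". The hypothesis under Specific Aims is directional: "We hypothesize that Keenoa will have higher response rate for those completing 3-day diet records". The plan does not say whether alpha is one- or two-sided, whether a continuity correction applies, or whether any allowance is made for loss. This is the only sample-size calculation in the document.

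**The concern.** The two rates, alpha, the target power and the test are enough to recompute the sample size under each reading of sidedness. A gap of 17.9 points, with rates between 60% and 80%, normally needs a good deal more than 50 per group.

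If the figure is wrong, the trial has much less chance of detecting its assumed effect than the plan states. A non-significant Aim 2 result could then be taken as evidence that Keenoa does not raise the response rate, because the design was described as having 80% power. The same figure is also offered as sufficient for Aim 1, which has no calculation of its own.

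**Working it through.** **Inputs** (all from the Power calculation paragraph, with the test from the Aim 2 analysis)

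- p1 = 0.621 (ASA24), p2 = 0.80 (Keenoa), difference d = 0.179
- alpha = 0.05, power = 80%, equal groups, chi-square test of two proportions
- Sidedness not stated. Two-sided is taken as the main case because the analysis tests for a difference. One-sided is shown beside it.

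**Step 1. Try to reproduce 50 per group.** The sample-size formula that corresponds to the uncorrected chi-square test is

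n = [z_α √(2 p̄(1−p̄)) + z_β √(p1(1−p1) + p2(1−p2))]² / d²

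- p̄ = (0.621 + 0.80)/2 = 0.7105, so √(2 × 0.7105 × 0.2895) = 0.6414
- √(0.621 × 0.379 + 0.80 × 0.20) = √0.395359 = 0.6288
- Two-sided: (1.960 × 0.6414 + 0.8416 × 0.6288)² / 0.179² = (1.2571 + 0.5292)² / 0.032041 = **99.6, so 100 per group**
- One-sided: (1.645 × 0.6414 + 0.8416 × 0.6288)² / 0.032041 = **78.3, so 79 per group**

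The other standard versions also fail to give 50:

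| Method | Two-sided, per group | One-sided, per group |
|---|---|---|
| Pooled variance | 100 | 79 |
| Unpooled variance | 97 | 77 |
| Arcsine | 99 | 78 |
| Pooled with continuity correction | 111 | 90 |

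No two-group version at 80% power comes near 50.

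**Step 2. Power at 50 per group.**

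Power = Φ{[d√n − z_α √(2 p̄(1−p̄))] / √(p1(1−p1) + p2(1−p2))}

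- Two-sided: (0.179 × √50 − 1.2571)/0.6288 = (1.2657 − 1.2571)/0.6288 = 0.014, and Φ(0.014) = **50.5%**
- Exact binomial enumeration, two-sided: **51.1%** for the uncorrected chi-square, **43.0%** for the Yates-corrected or Fisher test
- One-sided: **63.1%** by normal approximation, **64.1%** exact

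As a check on the answer of 100 per group, power there is 80.2% by the formula and 80.6% by exact enumeration of the uncorrected chi-square.

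**Step 3. What 50 per group can detect with 80% power.** Hold ASA24 at 62.1% and solve for the Keenoa rate, two-sided:

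- Uncorrected chi-square: 86.0% exact, 86.3% by the formula, a gain of about 24 points
- Yates-corrected: about 87.5%, a gain of about 25 points
- One-sided by the formula: about 84%, a gain of about 22 points

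**Step 4. Precision at 50 per group.** At the assumed rates, the half-width of a 95% confidence interval for the difference is 1.96 × √(0.395359/50) = 0.174. An observed 17.9-point gain would have an interval from about 0.5 to 35.3 points, which only just excludes zero. This agrees with power of about one half.

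**The case against.** **Sidedness.** It is not stated, and the hypothesis is directional, so 100 per group and 51% power should carry the label two-sided. That is fair. It does not save the plan's figure: one-sided, 50 is still 29 short of the 79 needed.

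**Approximation.** The opening sentence marks 50 as approximate. Rounding does not cover a factor of two, and the later sentence gives 50 as the required number without that mark.

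**A different method.** Three calculations land near 50: half of the 100 per group; a one-sample two-sided test against a fixed 62.1%, which gives 51.7; and the two-group formula with the power term left out, 1.2571²/0.032041 = 49.3. The documents do not show which, if any, was used. None of them sizes a two-group comparison for 80% power.

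**Scope.** The Aims statement puts acceptability and usability first and the response rate second. The numbers here measure Aim 2 power only. That limits the reach of the point but does not remove it, since the plan applies the same 50 to both aims.

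**Feasibility.** The trial is set to last 6 weeks and no recruitment rate is given, so 100 per group may not be attainable. That bears on which fix to choose, not on the arithmetic. A small trial is acceptable if its power is stated correctly.

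**Interpretation.** The plan does not say that a non-significant result will be read as no benefit. That is a risk, not a stated intention.

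**Conclusion.** The concern holds. On the plan's own inputs, 50 per group is about half the number required for the planned test taken two-sided: 100 per group, with 97 to 111 across standard methods. Power at 50 per group is about 51% (43% with a continuity correction) against the 80% stated. The chance of missing a true 17.9-point gain is therefore about 49%, not 20%. Under a one-sided reading the shortfall is smaller but still clear: 79 per group needed, and about 63% power.

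These figures treat participants as independent and assume no loss. The plan allocates the tool by week and gives no within-week correlation, so no adjustment is made here; positive correlation or loss would only raise the number needed. The 62.1% is described as completion of 3 days, without the energy-intake condition of the Aim 2 endpoint, so the true ASA24 rate for that endpoint could differ. That does not affect the check of the stated arithmetic.

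**What to change.** Correct the Power calculation paragraph, and state the sidedness and whether a continuity correction will be used. Two routes are open.

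1. **Keep about 50 per group and restate the power.** For a two-sided uncorrected chi-square test, say that power for 62.1% vs 80% is about 51%, and that the gain detectable with 80% power is about 24 points (62.1% vs about 86%). If a continuity correction is used, the figures are 43% and about 25 points. This costs SAP wording only and needs no extra participants; the price is a less favourable power statement.
2. **Keep the 80% power target and restate the size.** Say that about 100 per group, 200 in total, are required. This doubles enrolment and may not fit the 6-week period, which the sponsor would need to check against its recruitment rate.

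If enrolment stays at about 50 per group, it is also advisable to make the Aim 2 result the estimated difference in response rates with a 95% confidence interval, and to say that a non-significant test will not be read as no difference. The claim that 50 per group is enough for Aim 1 should be given its own basis or removed.

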Keenoa™ is an artificial intelligence-enhanced, image-assisted dietary assessment tool that has been originally designed to facilitate dietary data collection for dietitians and researchers.⁹ Serving as a visual food diary, individuals can upload a picture of their meal, choose the food items eaten using a preselected food list available by the app, and confirm the portion size with the presented visual aids. Two recent trials have aimed to evaluate the validity and usability of Keenoa™ against common methods of dietary assessment.^{10,11} In a randomized controlled trial of 72 Canadian adults, Keenoa™ performed better on analyzing group-level micronutrient intake relative to individual-level intake, suggesting its potential appropriateness for assessing dietary intake of the general population.⁹ In the same study, a greater proportion of participants preferred using Keenoa™ over a traditional pen-and-paper method (34.2% vs. 9.6%).⁹ Another randomized crossover trial with 136 participants showed that Keenoa™ has moderate to strong agreement, when compared against ASA24 recalls, in analyzing energy, macronutrient, and the majority of micronutrient intakes in both healthy adults and those with type 2 diabetes mellitus (T2DM).¹¹ In addition to Keenoa™, several image-based or image-assisted dietary assessment apps have been developed for research purposes.¹² With distinct interfaces, some of these apps, such as the mobile food record (used in All of Us Precision Nutrition study), require uploading pictures from specific distance or angle of the food to ensure precise portion size estimation, which in turn may impose burden on participants. Therefore, selecting proper technology-based instrument relies upon different factors including available resources, study objectives, study population,

etc.,¹² and we chose to assess the acceptability and feasibility of KeenoaTM in order to evaluate dietary habits in the Framingham Heart Study (FHS).

Specific Aims

We will assess the following aims in the FHS Third Generation-based cohort exam 4.

Aim 1: Evaluate acceptability of the Diet Tracking Smartphone Application KeenoaTM, and compare it to that of ASA24 diet records among older adults. We hypothesize that dietary assessment through KeenoaTM is more acceptable than ASA24, using quantitative satisfaction scale (0-5).

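### The chi-square named for Aim 1 does not test the difference in average 0–5 satisfaction that the plan says it will test

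*Combined protocol and SAP*

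**What the plan says.** The abstract puts acceptability first: "Primarily, we will assess acceptability and usability of Keenoa compared with the traditional, web-based Automatic Self-Administered 24-Hour (ASA24) Dietary Assessment Tool". Specific Aims, Aim 1, gives a directional hypothesis, "We hypothesize that dietary assessment through KeenoaTM is more acceptable than ASA24", measured on a 0–5 satisfaction scale that the plan itself calls quantitative.

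The whole of the Aim 1 analysis in the Statistical Analysis Plan is one sentence: "We will use chi-square to evaluate whether the average satisfaction rate (out of 5) of the two instruments" is significantly different. No cut-point, categories, ordered or trend version, effect estimate or confidence interval is given there or elsewhere.

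Aim 2 uses the same term for a completion percentage: "We will use chi-square to evaluate whether the response rates, defined as the percentage who completed 3 days of dietary assessment" and so on. There the outcome is binary and the test fits.

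On size, the Power calculation says "We estimate that we will require ~50 participants per group to complete aims 1 and 2". Its only inputs are response rates of 62.1% and 80%, which belong to Aim 2.

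**The concern.** The quantity to be compared is an average, but the test named is one for counts in categories. Taken in its usual sense, chi-square on whole-number 0–5 scores is a Pearson test on a 2×6 table with (2−1)(6−1) = 5 degrees of freedom. Its statistic stays the same if the score labels are shuffled, so it cannot isolate a difference in averages.

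The test can therefore mislead in two ways. It spreads its power over five contrasts and may miss a plain upward shift in satisfaction. It can also be significant when the averages are equal and only the spread differs, and that result could then be reported as a difference in acceptability. It does not say which tool did better, or by how much. This is the only analysis planned for the aim that the abstract lists first.

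The single term also leaves several analyses open (six categories, collapsed categories, a satisfied/not satisfied split, a trend test). They differ in power, and nothing prevents the choice being made after the data are seen.

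**Working it through.** **Inputs from the documents.** Score range 0–5; about 50 per group; alpha .05. **Assumed, because the documents are silent:** whole-number scores, independent participants, a two-sided test, and the score distributions below.

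**1. The plan's own figure.** The plan gives no figure for Aim 1. Its 50 per group comes from the Aim 2 rates. A two-sided comparison of 62.1% with 80% gives [1.960·√(2·0.7105·0.2895) + 0.842·√(0.621·0.379 + 0.80·0.20)]² / 0.179² = 99.6, so 100 per group, not 50. That is a separate matter and carries no weight here. For two means, 50 per group gives 80% power at a standardised difference of (1.960 + 0.842)·√(2/50) = 0.56. The plan states no satisfaction difference or SD to set against this.

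**2. Averages differ, Pearson misses it.** With equal group sizes, Pearson X² = Σ(a−b)²/(a+b). Take counts for scores 0 to 5 of 2/4/10/16/12/6 and 1/2/5/12/16/14:
- Means: 150/50 = 3.00 and 182/50 = 3.64.
- X² = 1/3 + 4/6 + 25/15 + 16/28 + 16/28 + 64/20 = 7.01, 5 df, p = 0.22. Shuffling the score labels leaves it at 7.01.
- t-test: p = 0.012.
- Linear-by-linear (trend) chi-square, (N−1)r² = 6.19, 1 df, p = 0.013.

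**3. Averages equal, Pearson rejects.** Take counts for scores 1 to 5 of 2/8/30/8/2 and 10/10/10/10/10:
- Both means are 150/50 = 3.0.
- X² = 64/12 + 4/18 + 400/40 + 4/18 + 64/12 = 21.1, 4 df, p = 0.0003.
- t-test: p = 1.0.

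**4. Power at 50 per group.** The second group has its cumulative odds divided by 2.5 (proportional odds). Each row is 20,000 simulated trials without continuity correction.

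| Base distribution, scores 0–5 | Mean | Pearson | Trend, 1 df | Welch t | Wilcoxon | Split at ≥4 |
|---|---|---|---|---|---|---|
| A: .03 .07 .15 .30 .30 .15 | 3.22 | .43 | .68 | .69 | .71 | .63 |
| B: .01 .03 .08 .20 .38 .30 | 3.81 | .43 | .64 | .65 | .69 | .49 |
| C: .10 .14 .18 .20 .20 .18 | 2.80 | .45 | .71 | .71 | .72 | .64 |
| D: .08 .17 .25 .25 .17 .08 | 2.50 | .44 | .72 | .72 | .72 | .58 |

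In A the shifted mean is 3.81. Analytic check for A: noncentrality 50·Σ(p−q)²/(p+q) = 6.18, giving 5-df power of .445 against the simulated .43. Also in A, Pearson against Welch is .25 against .46 at an odds ratio of 2, and .60 against .83 at 3. At 2.5, Pearson reaches .70 with about 85 per group, close to the .71 that Wilcoxon has with 50.

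**5. Equal means of 3.0, unequal spread, 50 per group.** First group: .02 .08 .20 .35 .28 .07 (SD 1.12).

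| Second group, scores 0–5 | SD | Pearson significant | Welch significant |
|---|---|---|---|
| .05 .10 .19 .27 .24 .15 | 1.37 | 19% | 5% |
| .06 .11 .18 .26 .20 .19 | 1.46 | 37% | 5% |
| .10 .11 .17 .18 .19 .25 | 1.64 | 77% | 5% |

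**The case against.** *The harm depends on a reading the plan does not state.* This is true for the size of the loss. If a 1-df trend chi-square is meant, the loss against Welch is at most about a percentage point. The word "rate" might also hint at a satisfied/not satisfied split, although an average on a quantitative scale points the other way. Neither reading rescues the sentence: the trend test is not named, and a split would compare proportions, not averages, at a cut-point that does not exist.

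*Nobody would analyse the 2×6 table as simulated.* In these scenarios 92–100% of the tables have an expected count below 5, so an analyst might collapse categories. Merging scores 0–2 raises Pearson power to about 51–54%. The gap to Welch shrinks but remains, and the collapsed test still rejects in about 21–73% of the equal-mean trials. The figure of 85 per group has the same limitation.

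*Pearson is not invalid.* Agreed: when the two distributions are identical it rejects 4.4% of the time in base A. The equal-mean rejections are correct as statements about distributions. They are wrong only as statements about averages, which is how the plan would use them.

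*The distributions and the odds ratio are invented.* They are assumptions with no basis in the documents, and the power figures are illustrations. The mismatch itself does not depend on them.

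*Other fixes would serve.* Also true. A rank test, an ordinal model, a named trend chi-square or a pre-defined proportion would each remove the ambiguity.

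**Conclusion.** The concern holds, and the Aim 1 sentence is wrong as written: the test named does not match the quantity it is said to compare. That conclusion needs only the plan's own text. It must be corrected because this is the sole analysis of the aim placed first.

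The size is conditional. If the unordered six-category test is used, with whole-number scores and 50 independent participants per group, the assumed shifts cost about 20 to 30 percentage points of power against Welch (.43–.45 against .65–.72). Equal averages with unequal spread can give significance in up to 77% of the constructed trials. These cases show what is possible, not what is likely. If a trend chi-square was intended, there is almost no loss, but the plan must say so and still needs an effect estimate.

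**What to change.** Replace the Aim 1 sentence with, for example: *Mean satisfaction (0–5) will be compared between Keenoa and ASA24 with a two-sided Welch t-test (alpha = .05). The mean difference (Keenoa minus ASA24) will be reported with its 95% confidence interval. A Wilcoxon rank-sum test will be a sensitivity analysis.* If another summary is intended, name its test, and any cut-point, before the data are seen.

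At 50 independent participants per group the interval half-width is 1.984·SD·√(2/50): 0.40, 0.50 or 0.60 points for an assumed SD of 1.0, 1.25 or 1.5. The Power calculation should either state the satisfaction difference and SD behind its claim to cover Aim 1, or report this expected precision.

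The change to the test takes a few lines of text and no extra data. Because the tool is randomised by week, clustering affects this replacement as it would any test that assumes independence. The half-widths above ignore it, and it needs separate work.
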